10.3.4 Procedure(s) to account for missing or spurious data

See section 7.7 for strategies to maximise follow-up and to prevent missing data.

When a patient withdraws from the study prematurely, all data collected up until the moment of withdrawal will be analysed (using the intent-to-treat approach). In case the data for measurement of the primary endpoint was not collected, the outcome will be classified as failure or continued benzodiazepine use in the intent-to-treat analysis. After withdrawal, no further data of this patient will be collected.

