7.4 Blinding

Owing to study procedures, patients and GPs will not be masked to their random allocation but GPs will be kept blinded to their allocation until after patient recruitment. The outcome assessors will be kept blinded to the allocation during the whole study until after data analysis.

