7.11 Withdrawal criteria

Withdrawal from the study can be initiated either by the patient or by the general practitioner.

As stated in the Informed Consent patients have the right to end her/his participation in the trial at any point in time and for any reason. In case a patient wishes to end her/his participation, she/he can do so either by notifying her/his GP or by ticking the box that will be provided in each e-questionnaire allowing patients to communicate their wish to withdrawal.

The treating GP can also consider a patient for withdrawal from the study. However, the GP will have to discuss this option with the study coordinator and to receive the consent of the latter before the final decision of withdrawal can be made.

In all instances, the reason for withdrawal will be asked for and notified.

Withdrawn patients will not be replaced. For statistical handling of withdrawn patients see section 10.3.4.

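### An unmasked GP, with the consent of a coordinator who also knows the allocation, can end a still-consenting patient's participation; trial data collection then stops and an uncollected 12-month urine test counts as continued use

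*Combined protocol and SAP*

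**What the plan says.** Section 7.11 knows one kind of withdrawal, from the study: "Withdrawal from the study can be initiated either by the patient or by the general practitioner". On the GP route it says "The treating GP can also consider a patient for withdrawal from the study", and requires the GP to discuss this with the study coordinator and "to receive the consent of the latter before the final decision of withdrawal can be made". No criteria for that decision are listed, and nothing makes it depend on the patient withdrawing consent. Reasons are kept: "In all instances, the reason for withdrawal will be asked for and notified". Both routes lead to the same rule: "For statistical handling of withdrawn patients see section 10.3.4".

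Section 10.3.4 keeps data collected up to withdrawal in the intent-to-treat analysis. If the primary endpoint was not collected, "the outcome will be classified as failure or continued benzodiazepine use in the intent-to-treat analysis". It ends: "After withdrawal, no further data of this patient will be collected".

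On masking, 7.4 states that "patients and GPs will not be masked to their random allocation", although GPs do not know the allocation during patient recruitment. Section 7.3.1 has the allocation reported to the study coordinator and the GP together.

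**The concern.** The primary endpoint is well protected in other respects: a laboratory urine assay (7.7), outcome assessors blinded until after analysis (7.4), and GPs blinded to urine results (7.7). The withdrawal rule opens a gap in that protection. For a patient withdrawn before the week-52 sample, the primary outcome is settled by a decision of two people who both know the arm, not by the assay. The patient may be entirely willing to give the sample.

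Two things are at stake. If such decisions are more frequent in one arm, the comparison of discontinuation rates is biased. If they are equally frequent, the observed difference shrinks and power falls. In addition, the later questionnaires and eCRF entries for these patients are lost, including the exploratory data on falls, withdrawal symptoms and patient-reported adverse effects (3.6, 7.7). If an adverse event prompted the withdrawal, the comparative record of harm stops just where it is of interest.

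The point is about the conduct rule that creates avoidable missing data. How unavoidable missing data should be analysed is a separate question.

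**Working it through.** **1. The chain of rules**

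| Step | Section | Content |
|---|---|---|
| Who can start withdrawal | 7.11 | Patient or GP; no criteria for the GP route |
| Check on the GP | 7.11 | Study coordinator must consent |
| Who knows the arm | 7.4, 7.3.1 | GP and coordinator both do |
| What follows | 7.11 to 10.3.4 | Same rule for every withdrawn patient |
| Data collection | 10.3.4 | Stops |
| Primary outcome | 10.3.4 | Failure, if the 12-month sample was not already collected |

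Section 10.3.4 speaks of a patient who withdraws, which alone might be read as the patient's own decision. The cross-reference in 7.11 covers withdrawn patients generally, so the GP route is included.

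**2. The plan's own sample size (10.1)**

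Inputs: 15% versus 25%, alpha 0.05, power 80%, 10% loss, ICC 0.11, cluster size 10. Two-sided testing is assumed, since 10.1 does not say.

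- Two proportions with continuity correction: 270 per group.
- Loss allowance: 270 x 1.10 = 297 per group, 594 in total, as stated.
- Design effect: 1 + 0.11 x (10 - 1) = 1.99; 594 x 1.99 = 1182.06, so 1182 patients and 119 GPs, as stated.

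**3. Simple illustration**

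The documents give no GP-withdrawal rate, so the share is an assumption. Take 600 patients per arm (1200 planned).

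- 5% of 600 = 30 withdrawn before the 12-month sample.
- If 15-25% of them would have tested negative: 30 x 0.15 = 4.5 to 30 x 0.25 = 7.5 successes scored as failures.
- Effect on the arm's rate: 4.5/600 = 0.75 to 7.5/600 = 1.25 points.
- With 10% withdrawn: 1.5 to 2.5 points.

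**4. Effect on the design comparison**

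Observed rate = true rate x (1 - w), where w is the share withdrawn and scored as failure, assumed unrelated to what the test would have shown. Effective n per arm = 1182/2/1.99 = 297; power without continuity correction.

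| Withdrawn and scored as failure | Control | Blended | Difference (points) | Power |
|---|---|---|---|---|
| None | 15.0% | 25.0% | 10.0 | 86% |
| 2%, blended only | 15.0% | 24.5% | 9.5 | 83% |
| 5%, blended only | 15.0% | 23.75% | 8.75 | 77% |
| 10%, blended only | 15.0% | 22.5% | 7.5 | 65% |
| 5%, control only | 14.25% | 25.0% | 10.75 | inflated |
| 10%, control only | 13.5% | 25.0% | 11.5 | inflated |
| 10%, both arms | 13.5% | 22.5% | 9.0 | 82% |

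**5. No true effect, withdrawal in control only (N = 1200)**

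| Share withdrawn | True rate | Spurious difference (points) | Two-sided rejection (nominal 5%) |
|---|---|---|---|
| 5% | 15% | 0.75 | about 6% |
| 5% | 25% | 1.25 | about 6.5% |
| 10% | 15% | 1.5 | about 8% |
| 10% | 25% | 2.5 | about 11% |

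**The case against.** The strongest reply is that the GP does not act alone. The GP may only propose withdrawal, and the coordinator's consent is needed before it is final. A reader might infer a unilateral power from the first part of 7.11, and the text does not support that. The check remains limited: the coordinator knows the allocation and no criteria bind the decision.

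Second, a reader might infer that ignoring the e-tool, or stopping a taper, leads to withdrawal from the study, and hence that the blended arm must lose more patients. The documents do not say so and lean the other way. Participation does not oblige a patient to discontinue (7.1.1), dose increases are recorded as ordinary GP actions (7.7), e-tool use is tracked (8.2), and a blended-arm subgroup analysis by e-tool use is planned (10.3.2), which presupposes that low users stay in. Nor do the documents state that the number of GP contacts differs by arm; follow-up in both depends on need. Imbalance is therefore possible, but neither its presence nor its direction is documented. This objection stands.

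Third, a reader might infer that all harm follow-up ends. Section 10.3.4 ends trial data collection only. Routine-care safety reporting (section 9) continues, and nothing suggests that the patient leaves the GP's care.

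Fourth, the assumed shares may be high. The only attrition figures in 10.1 are 7% at 12 months in a cited trial and a 10% planning allowance. A 10% GP-initiated share in one arm would exceed the first and match the second. Patients withdrawn because of trouble would plausibly have tested negative less often than their arm as a whole, which makes the loss smaller.

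Fifth, withdrawn patients stay in the intent-to-treat analysis with a defined outcome, so the analysis population is intact. That is correct. The defect is that an obtainable outcome is replaced by an assigned one.

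**Conclusion.** The concern holds in a limited form. By the plan's own rules, an unmasked GP with an unmasked coordinator's consent can end the participation of a patient who has not withdrawn consent. Trial data collection then stops and an uncollected 12-month test becomes a failure. The effect on the primary comparison can go either way.

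Its size is unknown, because no GP-withdrawal rate is given. At an assumed 5% in one arm, with 15-25% of those patients otherwise negative, that arm's rate moves by 0.75-1.25 points. At the design rates, 5% in the blended arm only takes the difference from 10 to 8.75 points and power from 86% to 77%. These figures assume that withdrawal is unrelated to the outcome the patient would have had. If none of the withdrawn patients would have tested negative, the loss is zero.

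The documents do not support reading this as a demonstrated bias against blended care or as an end to safety surveillance. It is an avoidable source of missing primary and exploratory harm data, worth closing because closing it costs little.

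**What to change.** In 7.11 and 10.3.4, state that trial data collection (the week 6, 12, 26 and 52 questionnaires and the week 26 and 52 urine samples) stops only when the patient withdraws consent to it. State also that a GP-initiated end of the trial intervention does not by itself end follow-up. Leave clinical decisions on treatment and taper as the protocol has them.

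The reason for withdrawal is already recorded. Add one item: whether an adverse event led to it. Reporting GP-initiated cases by arm would then show whether any imbalance arose.

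Cost: a short amendment with ethics review (13.1), possibly a line in the consent form, and one eCRF field. No new procedure is needed: the questionnaires are e-mailed, and the week 26 and 52 samples need no GP consultation (7.7). The patient can still refuse either.

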10.4 Data collection for economic evaluation

One of the goals of the KCE Trials programme is to improve the efficiency of the healthcare system. This protocol has been designed with a later possible economic analysis in mind, e.g. the necessary data to allow the conduct of a health economic evaluation will be collected. The planned economic analysis is briefly described below, together with the variables collected in this protocol for this purpose. For the sake of clarity, the economic analysis is not a part of this trial. The decision to conduct such economic analysis will depend on the effectiveness results of this trial.

OVERVIEW

The first part is a cost study with the aim to identify significant cost drivers. A cost driver is a component in the health service significantly associated with the costs. The potential subcategories of costs considered are (Carreras et al, 2016): acute outpatient, acute inpatient, primary care, residential care, pharmacy prescriptions, chronic prescriptions, diagnostic tests, accident & emergencies, intervention costs and total costs at 6 and 12 months. A health care payer perspective is adopted and includes payments out of the federal government's and the communities' health care budget as well as patients' co-payments.

The second part on the economic evaluation concerns cost-utility (CUA), comparing costs and consequences between participants in the 'blended care' study group (intervention group) and those in the 'leaflet information' study group (control group).

ANALYSES

Part I: cost estimations

In both study groups, the subcategory costs and total costs are calculated. In addition, between-group differences are calculated for each subcategory and total costs. First, descriptive statistics will provide unadjusted information on the magnitude and distribution of the 'blended care' costs for each of the subcategories compared to the 'leaflet information' group. Secondly, a generalized linear modelling (GLM) will be applied to evaluate the total costs between both groups adjusted for the other independent factors (patient characteristics, cluster, cost drivers etc).

Part II: health economic evaluation (CUA)

Bottom-up approach:

In this phase, an analysis of the costs and health effects alongside the clinical trial will be conducted. The costs include (1) the direct medical costs for which a nomenclature code exist, and (2) costs associated with the intervention (e.g. monetary valuation of caregiver time spent on the program, administrative costs). The effects will be expressed as 'utilities' (i.e. a health-related quality of life weight, range from 0 [dead] to 1 [perfect health]).

For both study groups, resource use data and health-related quality of life (HRQOL) data will be collected using information from the patients' medical records and using a questionnaire (self-reported) for those resources not captured by the medical records. Subsequently, information from the RIZIV nomenclature

database will be used to attach costs to the different resource use data. In the intervention group, the costs associated with the intervention will be collected using a pre-printed form that has to be filled out by the participating GPs. The HRQOL data will be collected using the EQ-5D-3L questionnaire (filled out by the participating patients).

Resource use data and health-related quality of life data will be collected at regular time points: at baseline, at six weeks, at 12 weeks, at 26 weeks, and at one year. Information related to the intervention costs will be collected during the intervention period. The latter costs will be recalculated at patient level.

The ratio of the incremental costs to the incremental utilities is called the incremental cost-effectiveness ratio (ICER) calculated as : $(\text{Cost}_N - \text{Cost}_C) / (\text{Health effect}_N - \text{Health effect}_C)$ ^a. This measures reflects the difference in costs per unit of effect (in this example: utility).

A well-known issue is the presence of missing data related to the different outcome variables (cost data, utility data). Different methods exist to handle this. In the current research project, single imputation methods will be used. In this method, the missing data are replaced with a single predicted value (e.g. the adjusted mean value) (Diaz-Ordaz et al. 2014). Sensitivity analyses will be conducted to determine how different input values will impact the outcome (Diaz-Ordaz et al. 2014).

Markov decision-analytic modelling:

A Markov decision-analytic model will be used to predict longer term patient outcomes and complications for patients in the 'blended care' arm versus the 'information leaflet' arm. The outcome considered as input for the Markov model will be the occurrence of falls. This kind of model allows us to simulate transitions in various health states beyond the duration of the intervention. Each health state is associated with costs and utilities. The health effects will be expressed as quality-adjusted life years (QALYs). QALYs are calculated by multiplying the utility level (information obtained in phase 1) with the number of years and individual lives with the condition. Input data for the Markov model will be obtained from phase 1 and from published literature.

Health economic evaluation studies are frequently characterized by some degree of uncertainty or methodological considerations. In the current study, one-way sensitivity analyses and probabilistic sensitivity analyses (non-parametric bootstrapping) will be conducted to handle this uncertainty.

[figure not shown]

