4 TRIAL DESIGN

This study is a pragmatic cluster randomised controlled superiority trial:

multi-centre: 6 academic centres of general practice will be involved in the recruitment of 120 GPs primary care practices

pragmatic: criteria excluding patients from participation will be limited as well as procedures that do not reflect care as usual

cluster: randomisation occurs at the level of the primary care practice while patients are the unit of analysis

randomised: block randomization per academic centre will be performed to assign primary care practices to either the intervention or the control arm

controlled: the intervention will be compared with usual care

superiority: the trial is designed to show that the intervention is superior to usual care

The rationale for choosing a cluster design is to prevent contamination across the intervention and control arm. The cluster and unit of randomization is the primary care practice. There will be 2 arms – the blended care arm and the usual care arm- in 50:50 ratio.

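### The planned model for total cost adjusts the arm comparison for cost drivers, which are parts of that total; with follow-up values, its arm coefficient does not estimate the difference in total cost

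*Combined protocol and SAP*

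**What the plan says.** All of this is in section 10.4 unless another section is named.

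- **Definition.** "A cost driver is a component in the health service significantly associated with the costs".
- **Candidate components.** The list, with times in months, reads "acute outpatient, acute inpatient, primary care, residential care, pharmacy prescriptions, chronic prescriptions, diagnostic tests, accident & emergencies, intervention costs and total costs at 6 and 12". It therefore holds eight care categories, the cost of the intervention, and the total itself.
- **Simple comparisons.** Part I states that "between-group differences are calculated for each subcategory and total costs". A first step is descriptive: "descriptive statistics will provide unadjusted information on the magnitude and distribution of the 'blended care' costs for each of the subcategories".
- **Model.** A GLM then serves to "evaluate the total costs between both groups adjusted for the other independent factors (patient characteristics, cluster, cost drivers etc"). Family, link, the choice of drivers, the time window of their values and the form of the cluster term are not given.
- **Timing of resource-use data.** Collection is "at baseline, at six weeks, at 12 weeks, at 26 weeks, and at one year".
- **Status.** "For the sake of clarity, the economic analysis is not a part of this trial". Whether it is done at all depends on the effectiveness results.
- **Design.** Section 4: "The cluster and unit of randomization is the primary care practice". Section 10.3.2 handles clustering in the primary analysis with a random effect by general practitioner.

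**The concern.** An adjustment covariate in a randomised comparison should not be affected by allocation. Cost drivers, as defined here, are the opposite: they are the channels through which the programme would change cost. If blended care shortens inpatient stays but adds consultations, both changes belong in the difference in total cost. Holding inpatient and primary care use fixed takes them out.

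Intervention costs are the clearest case. Section 10.4 collects them in the intervention group only, so as a covariate they are nearly a second copy of the arm indicator.

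At stake is the only adjusted between-arm cost comparison that Part I describes. Because drivers are those components found to be significantly associated with costs, the quantity estimated would depend on which ones the data select. It could disagree with the simple difference in total cost, and no rule says which of the two prevails.

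**Working it through.** Section 10.4 gives no cost estimate, so there is no figure of the plan's own to reproduce. The check is algebra, followed by an illustration with assumed costs.

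**1. Algebra (identity link).** Let total cost be T = ΣC_j, let Δ_j be the arm difference in mean of component j, and let Δ_T = ΣΔ_j. Least squares of T on arm and a set S of components fits the two arm means exactly, so

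arm coefficient = Δ_T − Σ_{j in S} b_j Δ_j,

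where b_j is the fitted slope of T on C_j.

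- If S holds every component, each b_j = 1 and the coefficient is Δ_T − Δ_T = 0, whatever the true difference.
- If S holds some components, unrelated within arm to the omitted ones, each b_j = 1 and the coefficient is the difference in the omitted components only.
- If included and omitted components are positively related, b_j exceeds 1 and more is subtracted.

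**2. Assumed inputs.** 120 practices of 10 patients (120 GPs with 10 patients each in the trial summary, each treated as one practice). Everything else is assumed.

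| Component | Control mean | Arm difference |
|---|---|---|
| Acute outpatient | 200 | −20 |
| Acute inpatient | 600 | −60 |
| Primary care | 250 | +40 |
| Residential care | 300 | −30 |
| Pharmacy prescriptions | 200 | −20 |
| Chronic prescriptions | 150 | −40 |
| Diagnostic tests | 100 | 0 |
| Accident and emergency | 120 | −20 |
| Intervention | 0 | +50 |
| **Total** | **1920** | **−100** |

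The care costs are skewed (gamma) and share a practice-level multiplier; 200 data sets were simulated.

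**3. Results.**

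| Model | Mean arm estimate | SD over runs |
|---|---|---|
| Identity link, no drivers | −107 | 101 |
| Identity link, all nine components | 0 (largest absolute value 3 × 10⁻¹²) | 0 |
| Identity link, three drivers (inpatient, residential, chronic prescriptions) | +59 | 44 |
| Exchangeable GEE by practice, no drivers | −107 | 101 |
| Gamma, log link, no drivers (cost ratio) | 0.946 | 0.051 |
| Gamma, log link, all nine (cost ratio) | 0.995 | 0.016 |

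- The model without drivers is consistent with the truth: its Monte Carlo error is 101/√200 ≈ 7, and −107 lies about one such error from −100.
- For three drivers, slopes of one would give −100 + (60 + 30 + 40) = +30. The shared practice effect raises the slopes: (59 + 100)/130 ≈ 1.22 on average, which gives +59.
- The spread falls from 101 to 44, or to 0, because the outcome is being explained by its own parts. That is not a gain in precision for the total.
- The true cost ratio is 1820/1920 = 0.948. The log link does not give exactly 1 with all components, but it removes nearly all of the difference.

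**4. Range over choices of driver.** With slopes of one, adjusting only for the components that rise (+40 and +50) gives −100 − 90 = −190. Adjusting only for those that fall (−20, −60, −30, −20, −40, −20, sum −190) gives −100 + 190 = +90. The same true difference of −100 can thus appear anywhere from −190 to +90, depending on what is selected.

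**5. Clustering.** Without drivers, exchangeable GEE leaves the estimate at −107 and raises the average standard error from 57 (naive) to 113, against an observed SD of 101. With practice indicators as fixed effects, the design matrix has 121 columns and rank 120, so arm cannot be separated from practice.

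**The case against.** **This is an outline of a possible later study.** The section calls its description brief, places the analysis outside the trial, and ends the covariate list with an open-ended etc. That stands, and it keeps the point minor. It does not make the listed covariates suitable.

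**Baseline values may be meant.** Resource use is collected at baseline too, and baseline use would be a sound covariate. The text does not exclude this. Nor does it say so, and the list of subcategories points the other way: it includes intervention costs, which cannot exist before allocation, and totals at 6 and 12 months. The concern applies where follow-up values are used.

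**The difference in total cost survives elsewhere.** Part I plans it separately from the model, and the formula for the incremental cost-effectiveness ratio makes no reference to the GLM. Both points stand. A reader might infer that the cost-utility result, or a reimbursement decision, would inherit the distortion. The documents do not link the ratio to this model, and section 10.4 mentions no reimbursement decision.

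**Clustering.** A reader might also infer that listing cluster among the adjusters is itself an error that removes the arm effect. That would be so only with practice fixed effects, which the plan does not specify; sections 10.3.2 and 10.3.3 use random effects. Accounting for practice is necessary in this design. All that can be asked is that the method be named.

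**Conclusion.** The concern holds for the cost-driver wording. If follow-up components enter the between-arm model, its arm coefficient is not the difference in total cost. Exact removal requires every component and an identity link. With a subset, or with another link, the result is a distorted contrast whose size and sign depend on the drivers chosen.

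A reader might take the 0, the +59 or the range of −190 to +90 as a forecast for this trial. They are not: every cost input is assumed, and the figures show only what the model can do to a known difference. The statement that the drivers are post-allocation also rests on a reading of an unspecified model, though it is the more natural one.

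The consequence is limited to one adjusted comparison in a conditional analysis outside the trial. No trial endpoint is touched, and the primary result is unaffected. This is a minor point, worth correcting because the correction is so cheap.

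**What to change.** In section 10.4, Part I:

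1. Remove cost drivers from the GLM that compares total costs between arms.
2. Limit adjustment to covariates that describe the period before allocation: patient characteristics and baseline resource use. Section 7.7 places the baseline visit after allocation, so the baseline window should be stated to end before it.
3. Report cost drivers in a separate descriptive analysis, without using it for the arm contrast.
4. State that practice is handled by a random effect, or by GEE or cluster-robust standard errors, in line with the random-effect approach of section 10.3.2, and not by practice indicators. State the family and link as well.

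The cost is a few sentences and no new data, since section 10.4 already schedules resource use at baseline. Section 7.6 does not itemise health-service use among the baseline data, so it is worth confirming that the medical records named in section 10.4 will supply it.

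### Section 10.4 fills missing costs and utilities with one predicted value, which understates the uncertainty of any cost-utility result unless imputation is repeated inside the bootstrap

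*Combined protocol and SAP*

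**What the plan says.** Section 10.4 (Part II, bottom-up approach) recognises that cost and utility data will be incomplete and sets one rule: "In the current research project, single imputation methods will be used". It explains that "the missing data are replaced with a single predicted value (e.g. the adjusted mean value"). The same paragraph adds: "Sensitivity analyses will be conducted to determine how different input values will impact the outcome".

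Further on, at the end of the Markov modelling text, the section says that "one-way sensitivity analyses and probabilistic sensitivity analyses (non-parametric bootstrapping) will be conducted to handle this uncertainty". It does not say whether the bootstrap resamples the incomplete data and imputes afresh each time, or resamples a data set that has been completed once. Multiple imputation is not mentioned.

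The section also limits its own standing: "For the sake of clarity, the economic analysis is not a part of this trial", and "The decision to conduct such economic analysis will depend on the effectiveness results of this trial".

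No other rule covers these variables. Section 10.3.4 imputes only the primary endpoint. Gaps are to be expected: under section 7.7, questionnaire answers not obtained by the deadline are missing, and under section 10.3.4 no data are collected after withdrawal.

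**The concern.** A deterministic predicted value carries no residual scatter, and filling it in once carries no allowance for having estimated it. If the completed data are then analysed as though every value had been measured, the spread of costs and utilities shrinks and the sample size is overstated. Both errors act in the same direction.

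This affects the uncertainty around both components of the ICER. The Markov model takes inputs from the trial-based phase, so the understatement can carry into the long-term results. A funder reading the economic report would see more certainty than the data support. Changing the input values tests how far the answer moves, but it does not restore lost variance.

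**Working it through.** Section 10.4 gives no figure to reproduce: no missing share, no interval, no precision target. The check asks how much precision is misstated over a plausible range.

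**Inputs**
- Missing share m: not given for costs or utilities. Assumed 10% to 40%. The 10% matches the loss to follow-up in section 10.1, but that figure was set for the sample size of the urine endpoint.
- Mechanism: missing completely at random (assumed).
- Strength of the predictor: not given. R² = 0 (plain arm mean) and R² = 0.5 are shown.
- Clusters: 60 of 10 patients per arm, from the 120 GPs with 10 patients each and 1:1 allocation.
- ICC: 0.11 from section 10.1, borrowed from the discontinuation outcome, and also 0.

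**Arm-mean imputation.** With n patients per arm and variance s², the estimate is really the mean of n(1 − m) values.
- Correct variance: s² / [n(1 − m)]
- Variance computed from the completed data: about s²(1 − m) / n
- Ratio of standard errors: 1 − m

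**Regression imputation with predictor strength R².**
- Ratio = √{[R² + (1 − m)(1 − R²)] / [R² + (1 − R²)/(1 − m)]}
- Example, m = 0.10 and R² = 0.5: √[(0.5 + 0.45) / (0.5 + 0.5/0.9)] = √(0.95/1.0556) = 0.949

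**Coverage of a nominal 95% interval:** 2Φ(1.96 × ratio) − 1. Example, arm mean and m = 0.10: 2Φ(1.764) − 1 = 0.922.

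| Missing | SE ratio, arm mean | Coverage | SE ratio, R² = 0.5 | Coverage |
|---|---|---|---|---|
| 10% | 0.90 | 92.2% | 0.949 | 93.7% |
| 20% | 0.80 | 88.3% | 0.894 | 92.0% |
| 30% | 0.70 | 83.0% | 0.837 | 89.9% |
| 40% | 0.60 | 76.0% | 0.775 | 87.1% |

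**Does the bootstrap repair it?** This was simulated with arm-mean imputation, normally distributed outcomes, 1,500 trials and 300 cluster resamples per trial. Coverage at ICC 0.11:

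| Missing | Impute once, then bootstrap | Impute inside each resample |
|---|---|---|
| 10% | 91.1% | 94.0% |
| 20% | 88.1% | 94.7% |
| 30% | 82.4% | 94.1% |
| 40% | 74.9% | 94.5% |

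With ICC 0 the pattern is the same: 91.5%, 86.0%, 80.7% and 74.7% when imputing once, against 93.5% to 94.4% when imputing inside each resample. A bootstrap of once-completed data reproduces the shortfall in the formula; repeating the imputation largely removes it. Multiple imputation was not simulated.

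**The case against.** The strongest reply is about scope. The section calls the economic work a later possibility, describes it briefly, and makes it depend on the effectiveness results. No trial endpoint uses the rule, and it does not alter what is collected, so a later economic plan could set the method without loss. This stands as a limit and keeps the severity low. It does not make the stated rule sound. Because the go-ahead depends on the results, a correction left until then would be made after they are known.

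Several stronger readings are tempting, and the documents do not support them:
- **That the bootstrap will be run on data imputed once.** The order is not stated. Single imputation redone in each resample would be largely valid, as the simulation shows.
- **That the method ignores practice clustering and the link between costs and utilities.** The predictors are not specified. The adjusted mean is only an example and could condition on arm or practice, and the cost model in Part I lists cluster among its adjusters. What can be said is that the imputation rule does not state that it respects them.
- **That 92%, 88% and 83% are the expected coverages.** They describe the least favourable case, an unadjusted arm mean. A useful predictor softens them, and resource use taken from medical records does not depend on questionnaire response.
- **That the ICER itself is wrong.** Under arm-mean imputation with data missing completely at random, the point estimate equals the available-case value. Only its stated uncertainty changes, and the section does not say how that will be displayed.

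The sensitivity analyses on input values do mean that the imputed values are not left unexamined, but they do not correct a standard error.

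**Conclusion.** The point holds at low severity. Section 10.4 prescribes a single predicted value for missing costs and utilities and includes no stated step that carries the imputation uncertainty forward. If such values are treated as observed, the standard error is about 90%, 80% or 70% of the correct one at 10%, 20% or 30% missing with arm-mean imputation, and about 95%, 89% or 84% with a predictor of R² = 0.5. Nominal 95% coverage falls to about 92%, 88% or 83% in the first case and 94%, 92% or 90% in the second. At 10% missing the shortfall is about 1 to 3 percentage points.

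These figures rest on assumed missing shares and on data missing completely at random; any other mechanism may add bias. A reader might infer that the trial's conclusions on discontinuation are affected. They are not, since the rule serves only the conditional economic analysis.

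**What to change.** In section 10.4, replace the single-imputation rule with one of two options:
- Multiple imputation, done by arm, respecting practice as the cluster and imputing costs and utilities jointly, with results combined by Rubin's rules. Baseline EQ-5D-3L, the utilities at each time point and the urine result are natural predictors.
- Imputation repeated within each resample of a bootstrap that draws whole practices.

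In either case, state how imputation and bootstrap are combined, and whether the bootstrap applies to the trial-based cost-utility analysis as well as to the Markov model. Keep a sensitivity analysis for departures from missing at random.

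This takes a few sentences in section 10.4, best written before the effectiveness results are known. It needs no extra data and no change to trial conduct; the only downside is more computing.
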